9.2.5 End of Study Clinical Form

The patient may withdraw from the study at any time for any reason. Research staff should only submit the End of Study form if the patient refuses all future direct and indirect follow-up on the study.

Study Calendar 10.

See below for a schedule of study assessments

	Baseline ¹	3 month	6 month	12 month	24 month
Patient questionnaires (min/max # questions based on skip pattern)					
Baseline Questionnaire (32/44)	Х				
Sociodemographic Follow-up (3)		Х	Х	Х	Х
Baseline Employment (18)	Х				
Follow-up Employment (14)			Х	Х	Х
FACT-G7 (7)	Х		Х	Х	Х
Self-Efficacy (6)	Х		Х	Х	
COST (11)	Х	Х	Х	Х	Х
Impact of Cost (31/41)	Х	Х	Х	Х	Х
Access and Utilization of Financial Resources (8)	Х	Х	Х	Х	Х
Acceptability (2)				Х	
Minimum/Maximum number of items at each time point	113/144	56/66	83/93	85/95	77/87
Site Completed Forms					
Site Survey ²	Х				
Baseline Clinical Form	Х				
Follow-up Clinical Form		Х	Х	Х	Х
24-month Follow-up Clinical Form					Х
End of Study Clinical Form					Х

Rev. Add1¹ Baseline study assessments must be completed within 14 days of registration. For participants who choose paper surveys, the date the survey was completed (date signed) must be within 14 days of starting radiation or chemotherapy.

² Each site with an individual CTEP ID is required to fill out one Site Survey within 30 days of the first participant enrollment.

11. Statistical Considerations

11.1 Sex and Ethnicity

Based on previous CDC data of 2009-2013 Colon and Rectum by Cancer Type and Race (age-adjusted) (66) the anticipated accrual in subgroups defined by sex and race is:

Ethnic Category	Sex		
	Females	Males	Total
Hispanic or Latino	20	23	43
Not Hispanic or Latino	252	268	520
Ethnic Category: Total of all subjects	272	291	563

Racial Category					
American Indian or Alaskan Native	2	2	4		
Asian	9	10	19		
Black or African American	35	34	69		
Native Hawaiian or other Pacific Islander	0	0	0		
White	223	242	465		
More than one race	3	3	6		
Racial Category: Total of all subjects	272	291	563		

11.2 Study Design and Objectives

This is a single-armed longitudinal study and the measurements of financial burden (COST score) will be collected at 5 time points over a 24-month follow-up time. The primary endpoint of this study is the change of COST score from baseline to the 12-month follow-up (FU) measurements.

11.3 Sample Size Considerations and Monitoring Plan

11.3.1 Stratification to be considered

The type of disease (colon versus rectal cancer) and the chemotherapy status (getting chemotherapy versus not getting chemotherapy) will serve as the stratification factors. Chemotherapy for these strata includes all intravenous and oral cytotoxic chemotherapy. For those with rectal cancer, those receiving chemotherapy combined with radiation will be considered in the "chemotherapy" strata. For the chemotherapy stratification, some patients may not know their chemotherapy plan at the time of registration. For this group of patients, the stratification will be implemented at the time of the 3-month follow-up. In addition, based on the stage distribution (Table 3 below), stratifying by receiving chemotherapy or not shouldn't be a bottleneck on patient's enrollment.

As illustrated in Table 3, it's expected the patients with colon and rectal cancers will be enrolled into the study at a ratio of 2:1 and the group of patients receiving chemotherapy versus patients not receiving chemotherapy will roughly equal to each other in the enrollment. Therefore, the accrual thresholds would be set up according to these ratios (Table 3), after the overall sample size is determined in the next section.

NOTE: Based on the actual enrollment as of 4/1/2019, the ratio of rectal cancer patients receiving chemotherapy versus not receiving chemotherapy is around 1:4. Thus, we accordingly changed the thresholds of these two strata.

Table 3: Stage distribution of colon and rectal cancer from SEER data (82).

Disease Type	Stage	Proportion*	Receiving Chemotherapy	Accrual Thresholds
	1 and 2	38%	Likely not	180-190
Colon cancer	3	37%	Getting Chemo	180-190
(70%)	4	21%	Excluding from study	None
	1 and 2	44%	Likely not	36-38
Rectal cancer	3	33%	Getting Chemo	144-152
(30%)	4	18%	Excluding from study	None

* The relative proportion of new cancer cases in US, 2016 (www.cancer.org).

11.3.2 Sample Size

Based on the data from previous cross-sectional studies (42, 50), we assume that the baseline COST score follows a normal distribution with the mean 25 and the standard deviation 12 and the 12-month FU score follows a normal distribution with the mean 22.5 and the standard deviation 12. Thus, the effect size of change is assumed to be 10%. The correlation between the baseline and the 12-month FU scores is assumed to be 0.2. Based on these assumptions, a sample size of 394 cancer patients will be needed to achieve a 90% power to detect the 2.5 difference (i.e., 10% change) at the 0.05 significance level using a two-sided Wilcoxon Signed-rank Test. These results are based on 20,000 Monte Carlo samples for the sample distributions under the null and the alternative hypothesis. The sample size will be 296 if the power remains at 0.90 and the correlation is assumed to be 0.4. A pilot study assessing financial burden among patients with advanced cancers had a 24% attrition rate between baseline and 12 month assessments, excluding those who died before the 12 month time point (36). An ongoing study on employment among cancer patients across the stage spectrum had a 30% attrition rate at the 12month follow-up ([name], personal communication). Therefore, we assume a 30% attrition rate at the 12-month follow-up and expect to enroll 563 patients into the study. Note: The imputation was based

on Monte Carlo samples in simulations, which caused slight fluctuations in the sample size. However, with 20,000 simulations, the fluctuation rate is only about 1%.

With these sample sizes, we will have the power of 1.0 to detect a difference of 5 (i.e., 20% change) from the baseline to the 24-month FU score, while the latter is assumed to follow a normal distribution with mean 20 and standard deviation 12. The above computations were done using PASS 14 (83).

Table 4: Power A	nalysis. Power:	0.80 and 0.90.	Correlation:	0.20 and 0.40.
------------------	-----------------	----------------	--------------	----------------

Power 0.797 (0.006) [0.791	N 292 0.802]	H0 Diff0 0.0	H1 Diff1 2.5	Corr R 0.200	Target Alpha 0.050	Actual Alpha 0.050 (0.003) [0.047	Beta 0.203 0.053]
0.803 (0.006) [0.798	218 0.809]	0.0	2.5	0.400	0.050	0.049 (0.003) [0.046	0.197 0.052]
0.900 (0.004) [0.896	394 0.904]	0.0	2.5	0.200	0.050	0.051 (0.003) [0.048	0.100 0.054]
0.904 (0.004) [0.900	296 0.908]	0.0	2.5	0.400	0.050	0.051 (0.003) [0.048	0.096 0.054]

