1.2.4 Preliminary Data for Assessing Financial Burden in Cancer Patients

Our study team has experience studying financial burden in cancer patients (5, 11, 12, 17, 34-42), and has specifically developed and utilized the COST measure (17, 42). In order to further test the validity, feasibility, and acceptability of longitudinally measuring financial burden using a validated measure of financial burden in cancer patients, our group completed a pilot study at Robert H. Lurie Comprehensive Cancer Center at Northwestern University (36). In this study, 96 patients with either a gastrointestinal, sarcoma, or lung cancer were longitudinally assessed over three months for both level financial burden (using COST, Incharge (43), and EORTC financial question) and health related quality of life. The COST score (described in more detail below) ranges from 0 to 44 with a score of 0 representing the highest financial toxicity and a score of 44 representing the lowest financial toxicity. In a population of both early and advanced stage disease, the mean COST score was 25.5 (SD 11.8) at baseline and there was no change in any of the financial burden measures at Assessment 2 (3 months after baseline). It is possible that no change was seen because this study did not follow patients long enough to see an increase in burden. Feasibility was

demonstrated with a 35% attrition rate. When accounting only for those that were alive to complete Assessment 2, attrition was 24%.

Acceptability of asking patient's questions regarding their financial situation were assessed in this pilot study with results summarized in Table 2. The majority of participants answered that they were either "somewhat" or "a lot" comfortable with answering questions about their financial situation and cost of treatment.

Acceptability question	Not at all (%)	A little bit (%)	Somewhat (%)	A lot (%)
How comfortable did you feel answering questions about your general financial situation?	6	12	29	53
How comfortable did you feel answering questions about how the cost of your treatment has affected your finances?	6	12	24	59
How comfortable do you feel discussing your finances and insurance with your physician?	12	24	35	29
How comfortable do you feel discussing your finances and insurance with a counselor?	0	24	24	53

Table 2: Acceptability of answering financially related questions.

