11.3.3 Accrual and Attrition Monitoring

It is expected that the monthly accrual for this trial will be approximately 15 to 16 cases, excluding the first 6 months as institutions obtain IRB approval. Therefore, we anticipate that 563 participants will be enrolled in about 3 to 3.5 years.

After assessing the preliminary data in [name]'s employment study (still ongoing), we didn't observe an obvious pattern of the dropout that associates with cancer type, stage, or employment status. Thus, we will not implement the adaptive design in our study. However, we will closely monitor the patient's attrition and then determine if the attrition rate will be significantly different among various groups. Accordingly, the protocol may be amended and the sample size may need to be adjusted to oversample patients for the groups with high attrition rates.

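### Does dating the pilot's 24% attrition at 3 months in one section and 12 months in another undermine the planned 30% loss and the enrolment of 563?

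*Combined protocol and SAP*

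**What the plan says.** Section 1.2.4 (Preliminary Data) describes a pilot of 96 patients, reference 36, assessed over three months. The stage mix is given by "In a population of both early and advanced stage disease". On outcome it reports that "there was no change in any of the financial burden measures at Assessment 2 (3 months after baseline"), and it offers a reason: "It is possible that no change was seen because this study did not follow patients long enough to see an increase in burden". Overall attrition was 35%. On survivors it adds: "When accounting only for those that were alive to complete Assessment 2, attrition was 24" per cent.

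Section 11.3.2 (Sample Size) also cites reference 36, but as "A pilot study assessing financial burden among patients with advanced cancers" that "had a 24% attrition rate between baseline and 12 month assessments, excluding those who died before the 12 month time point". The next sentence gives a second precedent: "An ongoing study on employment among cancer patients across the stage spectrum had a 30% attrition rate at the 12month follow-up", sourced to a personal communication. The section then assumes 30% loss at 12 months and sets enrolment at 563.

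Section 11.3.3 (Accrual and Attrition Monitoring) calls the employment study's data preliminary. It undertakes to monitor patients' "attrition and then determine if the attrition rate will be significantly different among various groups", and it allows for a protocol amendment and a sample-size adjustment to oversample groups with high loss.

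**The concern.** The shared reference, the identical 24% and the shared exclusion of deaths all suggest one pilot described in two ways. A study that assessed patients over three months cannot supply a 12-month rate. Section 1.2.4 is coherent on this point, since it explains the flat scores by short follow-up.

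The stake would be the credibility of the 30%. As section 11.3.2 reads, 30% sits six points above a pilot measured at the same 12 months. If the pilot ran only three months, that comparison disappears. One 12-month precedent remains, from a study still in progress. A 24% loss among survivors by three months would also make 30% by twelve months look less cautious. If true loss were well above 30%, fewer than 394 participants would provide the paired COST scores that the primary test needs.

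**Working it through.** **Inputs.** From section 11.3.2: COST mean 25 at baseline and 22.5 at 12 months, SD 12 at both, correlation 0.2 (0.4 as the alternative), two-sided alpha 0.05, Wilcoxon signed-rank test, 394 completers for 90% power, 30% attrition, 563 enrolled. From section 1.2.4: pilot attrition 35% overall and 24% among those alive.

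**1. Reproduce the plan's figures.** SD of the change = 12 × √(2 × (1 − 0.2)) = 15.18. The paired normal formula gives [15.18 × (1.960 + 1.282)/2.5]² = 387.3, so 388; the exact paired t calculation gives 390. A simulation of the signed-rank test (20,000 samples) at 394 gives power of about 0.89, against the 0.900 in Table 4. Enrolment is 394/(1 − 0.30) = 562.9, so 563. The plan's numbers hold up.

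**2. Does the 24% enter the calculation?** With 24% the result would be 394/0.76 = 518.4, so 519, and 563 − 519 = 44. The plan's 563 is reached only with 30%, which is the employment study's stated 12-month rate. Moving the pilot's 24% from month 12 to month 3 changes no term in the calculation.

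**3. Set the two accounts side by side.**

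| | Section 1.2.4 | Section 11.3.2 |
|---|---|---|
| Reference | 36 | 36 |
| Loss, deaths excluded | 24% | 24% |
| Time point | 3 months | 12 months |
| Patients | early and advanced disease | advanced cancers |

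The time points conflict. The stage descriptions conflict less clearly: section 11.3.2 does not say that all patients had advanced disease, and the pilot in section 1.2.4 did include such patients, so this may be loose description. A misnumbered citation is also possible. Section 11.3.2 cites reference 50 for COST data, but that entry is the Work Ability Index, and section 7.1.1.1 cites 36, 42 and 47 for the same assumption. Sections 11.3.1 and 11.3.2 also cite references 82 and 83, while the list ends at 68.

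**4. What if 12-month loss is not 30%?** Completers are 563 × (1 − loss), rounded down. Power is from simulation of the signed-rank test for a 2.5-point change. The 40%, 50% and 67% rows are assumptions, not figures from the documents.

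| Loss at 12 months | Origin | Enrolment for 394 completers | Completers from 563 | Power, correlation 0.2 | Power, correlation 0.4 |
|---|---|---|---|---|---|
| 24% | pilot, deaths excluded | 519 | 427 | 0.91 | 0.97 |
| 30% | employment study; planned | 563 | 394 | 0.89 | 0.96 |
| 35% | pilot, all causes | 607 | 365 | 0.87 | 0.94 |
| 40% | assumed | 657 | 337 | 0.84 | 0.92 |
| 50% | assumed | 788 | 281 | 0.76 | 0.88 |
| 67% | 24% lost every 3 months: 1 − 0.76⁴ | 1181 | 187 | 0.60 | 0.72 |

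Across the rates that the documents themselves report (24% to 35%), power at the less favourable correlation runs from 0.91 to 0.87.

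**The case for a change.** The strongest case for acting is that section 11.3.2 presents both precedents and then draws its 30% from them, so a reader is entitled to both being sound. If section 1.2.4 is correct, the 30% rests on one personal communication about unfinished work, and the pilot points to faster loss than the plan assumes. Section 11.3.3 ties a sample-size change to differences between groups, so a uniform shortfall would meet no stated comparison. Correcting the wording would cost almost nothing.

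Part of this stands. The two sections do disagree, and on the section 1.2.4 account only one 12-month source remains. It is also fair that 30% is the higher rate only within section 11.3.2, since section 1.2.4 reports 35% overall.

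The rest does not carry the point to a change. Section 11.3.2 never calls 30% conservative relative to the pilot; it lists two rates and adopts one. The 35% includes deaths in a pilot with advanced disease, whereas this study enrols stage I to III patients with a life expectancy of at least 24 months (section 4.1). The 67% case needs 24% loss to recur every quarter, which nothing in the documents supports and which lies far above the one 12-month rate not in dispute. On monitoring, section 11.3.3 already commits to close tracking of attrition. A sentence comparing overall completion with 70%, with no action attached, would add only a tabulation of returned 12-month forms that close tracking yields anyway.

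**Conclusion.** No change to the plan. The discrepancy is real but clerical: a precedent that was cited and then not used carries two different dates and two descriptions of its patients. The attrition allowance comes from the employment study's 12-month rate, and 394/0.70 = 563 is the same under either account of the pilot. Reconciling the wording would alter neither the number enrolled nor the analysis and conclusions of the study.

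This rests on two assumptions: that the employment study's 30% is correctly reported as a 12-month figure, and that it is a reasonable guide for curative-intent patients. The documents cannot confirm either. If loss were as high as the pilot's all-cause 35%, simulated power would fall by about two points, from 0.89 to 0.87 at correlation 0.2. An assumed 40% would give 0.84. Which account of the pilot is right cannot be settled without reference 36, and the design does not depend on the answer.

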11.3.3 Accrual and Attrition Monitoring

It is expected that the monthly accrual for this trial will be approximately 15 to 16 cases, excluding the first 6 months as institutions obtain IRB approval. Therefore, we anticipate that 563 participants will be enrolled in about 3 to 3.5 years.

After assessing the preliminary data in [name]'s employment study (still ongoing), we didn't observe an obvious pattern of the dropout that associates with cancer type, stage, or employment status. Thus, we will not implement the adaptive design in our study. However, we will closely monitor the patient's attrition and then determine if the attrition rate will be significantly different among various groups. Accordingly, the protocol may be amended and the sample size may need to be adjusted to oversample patients for the groups with high attrition rates.

11.3.4 Recruitment and Retention Plan

We will learn from the experiences of the ongoing SWOG 1417CD trial investigating financial burden in metastatic disease.

In addition to site visits and available phone and email support, as outlined above, the EASEE-PRO system will send email notifications and up to 3 follow-up reminders to notify web-based participants to complete surveys. Mail-based participants will receive surveys in the US mail as well as follow-ups for delinquent surveys. With both types of delivery, excessively delinquent participants may receive a phone call from the OEUA to determine if there is a problem completing the surveys. In the event that participants are unreachable by the OEAU,

Rev. Add1

the OEAU will coordinate with the site CRA in an effort to contact and retain participants.

Rev. Add1

11.3.5 Interim Analysis

To assess the survey burden, we will provide the NCI an interim report to analyze the range and median time to completion for the totality of the baseline questionnaires. Survey completion time will be determined from the meta-data collected form patients who opt to complete the survey online. This will be reported to the NCI within 90 days of the first 50 patients completing the questionnaire.

11.4 Statistical Analysis Plan

11.4.1 Primary Objective

The primary aim is to evaluate the change in the level of self-reported financial burden from baseline (within 60 days of diagnosis) to 12 months after diagnosis of colon or rectal cancer treated with curative-intent.

We will calculate the difference of COST measurements from baseline to 12-month FU for the completers who provide data at both time points, and use the paired t-test to assess if the mean difference is significantly different from zero. In case the data are not normally distributed, nonparametric methods (e.g., Wilcoxon signed-rank test) will be used instead to assess the difference. For the participants with missing measurements at one time point, we will implement the methods as described in Section 11.4.3 to handle the missing values. The two results will be compared as a sensitivity analysis.

In addition, linear regression models with the change of COST from baseline to 12-month FU as the response variable will be fit to investigate the impact of other factors, including demographics variables (e.g., age, sex, marital status), clinical variables (e.g., stage of disease, malignancy type, chemotherapy status), baseline questionnaire variables (e.g., self-efficacy,). The three-level treatment status (IV chemotherapy, chemotherapy without IV, and no chemotherapy) will also be evaluated as a predictor. The impact of system level variables (including being designated a minority/underserved site or not, availability of financial resources for patients) will be examined in the regressions as well. Since pregnant women may have higher health-care related costs, the response will be compared between pregnant women and the others; if significant, the subset analysis may be performed in this population.

- 11.4.2 Secondary Objectives
 - 11.4.2.1 Evaluate reported access and utilization of financial services (i.e. financial counselor, navigator, social workers) and its association to financial burden in the first 12 months after diagnosis of colon or rectal cancer treated with curative-intent.

The 8-question CCVI measure as described in Section 7.1.2 will be analyzed to evaluate the change from

baseline to 12-month FU. For the continuous item variable, we will conduct the paired t test to examine the difference if the distribution is normal. If not normally distributed, Wilcoxon signed rank test will be used. For the categorical item variable, the paired proportion test (e.g., McNemar test) will be used instead. The association between CCVI and COST measures will be evaluated using the Pearson or Spearman correlation coefficient.

Because we are aware that there is not a "gold standard" financial burden measure, we will include two other measures that have been used previously; (1) a series of items (Impact of cost questions) that are being used in the ongoing S1417CD; and (2) a single item in EORTC Q30 as our secondary endpoints. We acknowledge potential discrepancy between measures. Therefore we will conduct sensitivity analyses around the primary endpoint using the other measures and explore potential sources of discrepant outcomes.

11.4.2.2 Evaluate the change in level of self-reported financial burden and employment limitations from baseline (within 60 days of diagnosis) to 3, 6, and 12 months after diagnosis of colon or rectal cancer treated with curativeintent.

> The measurements of employment limitation by WPAI: SHP, WAI and WACS as described in Section 7.1.3 will be analyzed as continuous variables to evaluate the change from baseline to 3, 6, and 12-month FU. If the distributions are normal, we will conduct the paired t tests to examine the differences of these variables. If not normally distributed, Wilcoxon signed rank tests will be used. The association with COST measures will be evaluated using the Pearson or Spearman correlation coefficients.

11.4.2.3 Evaluate long-term outcomes at 24 months after diagnosis including financial burden, employment limitations and adherence to clinical follow-up guidelines.

To evaluate the change of financial burden from baseline to the other time points (i.e., 3-month, 6-month, and 24month), the similar approaches described for the primary objective's assessment will be implemented. In addition, longitudinal data analysis will be conducted to estimate the measurements' trajectory across all five times points. Specially, linear (or generalized linear) mixed model will be fit to study the change in the mean response over time and also the effects of cancer type, stage, treatment plan and demographics, etc. on financial burden. In case the changes in the mean response over time are not linear, the quadratic trends or non-linear trends via spline may be considered in the modeling (61). Interactions will be evaluated as well. The above analyses may be repeated to explore the categorized COST measures (63, 64).

Logistic regressions will be fit to study whether or not the level of financial burden will impact the patient's adherence to clinical follow-up guidelines, which is defined as follows: "adherent" is defined as completing all of the follow up guidelines within the 24 month study period and includes an endoscopic evaluation of their colon or barium enema, routine history and physical at least twice, and serum carcinoembryonic (CEA) level checked at least twice. The details of adherence questions can be found in Section 9.2.4.1.

11.4.2.4 Evaluate the change of quality-of-life outcome (QoL) from baseline to 12 months and its association with predictors

FACT-G7, as described in Section 7.1.4, will be analyzed to evaluate the change of QoL from baseline to 12 months. The sum of the 7-item scores will be modeled as a continuous variable in the linear regressions (57). The predictors will include demographics (age, sex, marital status), clinical variables (stage of disease, malignancy type, chemotherapy status), and financial variables (COST score). Similar to the primary aim assessment, the impact of the baseline questionnaire variables (e.g., self-efficacy) and the system level variables (including being designated a minority/underserved site or not, availability of financial resources for patients) will be examined in the models as well. FACT-G7 at 6 months will be included as an adjustment covariate. Similar analysis will be conducted to evaluate the change of FACT-G7 from baseline to 24 months as well.

11.4.2.5 Evaluate the change in level of self-reported financial burden from baseline to 12 months utilizing alternate measures of financial burden (i.e. impact of cost questions and single item from EORTC Q30)

> Because there is not a "gold standard" financial burden measure, we will include two other measures that have been used previously; (1) a series of items (Impact of cost questions) that are being used in the ongoing S1417CD; and (2) a single item in EORTC Q30 assessing the impact of medical treatment on finances. We acknowledge potential discrepancy between measures. Therefore we will conduct sensitivity analyses around the primary endpoint using the other measures and explore potential sources of discrepant outcomes.

> Similar approaches as used in the primary aim will be conducted to evaluate the changes of these two measures from baseline to 12 months.

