11.4.3 Handling Missing Data

As stated in the Section 11.3.3, we will closely monitor the patient attrition and determine whether the dropout is informative or not. If the missing is random, we may implement the method like multiple imputation to impute the missing values. In case the missing is not random (e.g., patients who are lost to follow up may experience more financial burden), we will implement various methods for the adjustment in our analysis, e.g., Bayesian modeling with informative priors. Analysis under different scenarios will be conducted to explore sensitivity to different missing data assumptions (65).

Since the COST is an 11-item PRO measure of financial toxicity, it is likely that partial data might be collected from some patients. According to the FACIT guidelines (www.facit.org), the patients who answer less than 6 out of 11 items will be excluded from the analysis. For patients who answer more than 6 but less than 11 items, the normalized score will be recorded according to the following formulae:

(sum of individual item scores)* 11 / the number of items answered.

12. Electronic Data Capture

Please refer to the EAQ162CDForms Completion Guidelines for the forms submission schedule. Data collection will be performed in Medidata Rave and EASEE-PRO.

This study will be monitored by the Clinical Data Update System (CDUS) version 3.0. Cumulative CDUS data will be submitted quarterly from the ECOG-ACRIN Operations Office – Boston to CTEP by electronic means.

13. Patient Consent and Peer Judgment

Current FDA, NCI, state, federal and institutional regulations concerning informed consent will be followed.

14. References

- 3. De Souza JA. The cost of cancer care: there is more than one elephant in the room. Oncology. 2012; 26: 926-8.

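### On its ordinary reading, section 11.4.1 rests the 12-month COST answer on completers, and section 11.4.3 picks its missing-data method by a test the data cannot settle

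*Combined protocol and SAP*

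**What the plan says.** Section 11.4.1 takes the difference in COST from baseline to 12 months "for the completers who provide data at both time points, and use the paired t-test to assess if the mean difference" is zero, with a Wilcoxon signed-rank test if the data are not normal. It then says: "For the participants with missing measurements at one time point, we will implement the methods as described in Section" 11.4.3, and "The two results will be compared as a sensitivity analysis".

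Section 11.4.3 makes the method depend on the type of missingness. On one branch: "If the missing is random, we may implement the method like multiple imputation to impute the missing values". On the other: "we will implement various methods for the adjustment in our analysis, e.g., Bayesian modeling with informative priors". Its example of the second branch is that "patients who are lost to follow up may experience more financial burden". It adds: "Analysis under different scenarios will be conducted to explore sensitivity to different missing data assumptions". It names no imputation variables, priors or shift values, and gives no rule for choosing the branch.

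Section 11.3.2 sets the scale of the loss: "we assume a 30% attrition rate at the 12-month follow-up and expect to enroll 563 patients into the study". COST is scheduled at all five visits (sections 7.1.7 and 10). A mixed model on COST is planned in section 11.4.2.3, but under a secondary objective and as a time trend, not as the baseline-to-12-month contrast.

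**The concern.** The ordinary reading is that the study's main answer comes from patients with both scores, and that everything else is a comparison. That has two consequences.

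- **Efficiency.** Even if dropout is completely random, the test ignores the baseline scores of about 169 patients and every 3- and 6-month score.
- **Bias.** If dropout is related to change in COST, the completers' mean change is not the cohort's. The test can then show a change that is not there or hide one that is.

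Section 11.4.3 is meant to guard against the second, but its switch cannot be operated as written. Observed scores can show that dropout is related to earlier COST. They cannot show that it is unrelated to the 12-month score nobody saw. The choice of branch would therefore be a judgement, possibly made after the completers' result is known.

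**Working it through.** **Inputs from section 11.3.2:** SD 12 at both visits, correlation 0.2 (alternative 0.4), difference 2.5, two-sided alpha 0.05, 90% power, 394 evaluable, 30% attrition, 563 enrolled. **Assumed, not in the documents:** every link between dropout and COST, and the correlations involving the 3- and 6-month scores.

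**1. The plan's figures.** SD of the difference = 12 × √(2 × 0.8) = 15.18. n = (15.18 × (1.960 + 1.282) / 2.5)² = 388, or 390 with the exact t distribution, against 394 stated. Simulated signed-rank power at 394 is 0.892, against 0.900. Enrolment: 394 / 0.70 = 562.9, so 563. The sample size is not in question. Of 563, 0.70 × 563 = 394 enter the test and 169 do not.

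**2. Completely random dropout, correlation 0.2.**
- Completers: SE = √(144 × 2 × 0.8 / 394) = 0.765; power at 2.5 = 0.905.
- Adding only the dropouts' baselines (likelihood estimate): SE = √(144 × (0.96/394 + 0.64/563)) = 0.717; power = 0.936.
- Variance ratio 0.585 / 0.515 = 1.136, and 394 × 1.136 = 448: worth about 54 extra completers.
- Adding the 3- and 6-month scores gives SE 0.705 to 0.717 and power 0.935 to 0.942 across three assumed correlation patterns (simulated).

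**3. Dropout that depends on baseline COST alone, no true change.** Let dropout differ below and above the mean baseline score, 30% overall. The completers' baseline gap is 12 × √(2/π) × (retention difference) / (retention sum). For 35/25 this is 9.575 × 0.10 / 1.40 = 0.684. False change = -(1 - correlation) × gap.

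| Dropout below/above mean | Baseline gap | False change, 0.2 | Rejection | False change, 0.4 | Rejection |
|---|---|---|---|---|---|
| 32/28 | 0.27 | -0.22 | 6% | -0.16 | 6% |
| 35/25 | 0.68 | -0.55 | 11% | -0.41 | 10% |
| 40/20 | 1.37 | -1.09 | 30% | -0.82 | 24% |

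In four-visit simulations at correlations 0.2 and 0.4, the repeated-measures model stays within 0.02 of zero with 4.4% to 5.7% rejection. That is by construction, since dropout there depends only on observed scores. When dropout follows the most recent observed score instead, the completers' bias at correlation 0.2 is -0.17 to -0.19 (35/25) and -0.38 (40/20), about a third of the tabled values.

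**4. Dropout that depends on the unseen 12-month score, no true change, correlation 0.2.** This is the plan's own example.
- Two visits, 35/25: completers 0.8 × 0.684 = +0.55; likelihood estimate about 0.96 × 0.684 = +0.66.
- Two visits, 40/20 (simulated): +1.10 and +1.32, with rejection 30% and 45%.
- Four visits, 35/25, model against completers (simulated): 0.64 v 0.55 (all correlations 0.2); 0.56 v 0.53 (0.5/0.35/0.2 by lag); 0.51 v 0.51 (0.6/0.4/0.2 by lag); 0.51 v 0.40 (all 0.4).

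So the model ranges from no better to clearly worse. Each 1-point shift of the missing 12-month scores moves the mean change by 0.3. The shifts that undo the two-visit likelihood biases are -0.66/0.3 = -2.2 and -1.32/0.3 = -4.4.

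**5. Why both signs are needed.** With SE held at 0.717, an estimate of -2.5 loses significance at a shift of (2.5 - 1.96 × 0.717)/0.3, about +3.6. An estimate of -1.0 gains it at (1.0 - 1.96 × 0.717)/0.3, about -1.4.

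**The case against.** The strongest reply is that the plan already deals with this in kind. It commits to applying section 11.4.3, names multiple imputation, Bayesian models and scenario analyses, and recognises that lost patients may be worse off. It monitors attrition by group (11.3.3), makes retention efforts (8.2.2, 8.2.3, 11.3.4) and inflates enrolment for 30% loss. Section 11.3.3 reports no obvious dropout pattern in another study's preliminary data. The power gain is modest, and in the plan's own example the repeated-measures model is no improvement.

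Much of this stands. But inflation protects power, not against bias. Retention may reduce loss without changing whom the test uses. The reassurance in 11.3.3 covers cancer type, stage and employment status, not COST. The point about the model is right, which is why the shift analysis is part of the fix.

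Four stronger readings are tempting and not supported:
- **That the plan declares the completers' test primary.** It labels neither result primary and does not say which prevails if they differ; this is inference from the sensitivity wording.
- **That the completers' result is shown to be biased.** No document links dropout to COST, and a weak link (32/28) hardly matters.
- **That (1 - correlation) of any baseline gap turns into change.** This holds only if dropout depends on baseline alone. With 35/25 dropout driven by the 12-month score, the baseline gap is about 0.2 × 0.684 = +0.14. The rule predicts -0.11, while the actual bias is +0.55.
- **That a mixed model cures the problem.** Step 4 shows that it does not when dropout depends on the unseen score.

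**Conclusion.** The concern holds as a weakness in the choice and specification of the analysis, not as a demonstrated error in the result. It is worth fixing before the data are analysed.

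Under completely random dropout the cost is efficiency only: SE 0.765 rather than 0.717, power 0.905 rather than 0.936, at SD 12, correlation 0.2 and 30% loss. Under dropout linked to baseline COST the false change could be negligible (-0.22) or as large as -1.09, which is 44% of the planned 2.5-point effect. It is about a third of the 35/25 and 40/20 values if dropout tracks the latest observed score. All these links are assumed.

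Under dropout driven by the unseen 12-month score, neither the completers' test nor the model is safe, and only a stated range of shifts shows how far the conclusion depends on the missing patients. No calculation here covered deaths or patients of unknown vital status.

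**What to change.** 1. **Section 11.4.1.** Name as primary the baseline-to-12-month contrast from a repeated-measures model on COST at baseline, 3, 6 and 12 months: categorical time, unstructured covariance, all patients with at least one score. Keep the completers' t-test or Wilcoxon as a sensitivity analysis.
2. **Section 11.4.3.** Replace the random/not-random switch with one stated imputation model: 12-month COST from baseline, 3- and 6-month COST, disease type and chemotherapy status. Add a pre-specified two-sided shift of the missing 12-month scores, for example -5 to +5 in 1-point steps. Report it beside the primary result, with the shift at which the conclusion changes. That range covers the -2.2 and -4.4 found above.
3. **Deaths.** State that no score is imputed or shifted after a recorded death, and report deaths separately; vital status is on the Follow-up Clinical Form (9.2.3). Say also how patients who die before 12 months, or whose vital status is unknown, enter the model.

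The cost is SAP wording and a little programming. No new data or patients are needed. The downsides are reliance on missing at random given observed COST, which is why the shift analysis is not optional, and loss of the Wilcoxon fallback for the primary result. Large-sample normality of the mean is a reasonable basis with about 394 or more patients.
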